Statistical Analysis Plan

Protocol Title: A randomized, double-blinded and placebo-controlled study on super-oxygenated water

Protocol Number: Inhale-001

ClinicalTrials.gov ID: NCT07016191

Principal Investigator:

[name].

[name]
[name]
[name]
United States

[contact]
[contact]

Sponsor:

Inhale, Inc

[name]
[name]
United States
[contact]

INTRODUCTION

The aim of this project is to test in a single-center randomized clinical trial, if ingestion of INHALE super-oxygenated water can augment blood oxygen saturation (SpO₂) and reduce heart rate (primary outcome measures) compared to their pre-ingestion levels as well as boost energy level and brain clarity (secondary outcome measures).

This statistical analysis plan (SAP) will give more detailed descriptions of the endpoints in the study and the corresponding analyses.

STUDY DESIGN

A total of 60 consenting subjects (research participants) will be recruited in the study. The study is a parallel-group clinical trial between two study arms to receive either INHALE super-oxygenated water (test article) or a source and taste-matched normal water (placebo control) randomized at 1:1 ratio with each arm enrolling 30 subjects. This is a double-blind study where neither the subject nor the investigator will know the assigned treatment. An unblinded research staff will perform the randomizations and dispense the blinded waters for use by blinded investigator.

The subjects will ingest 12 oz of water (about 10% of daily fluid intake which is similar to an average beverage size) in one administration. This amount is based upon available literature as a reasonable amount of fluid to drink and is aimed at not causing any dilution effect on blood oxygen saturation. The test article, INHALE water, contains dissolved oxygen at ~56 mg/L without any added sodium, sugar, protein or fat. The source and taste-matched normal water is packaged in the same way as the test article and contains dissolved oxygen at 0 mg/L without any added sodium, sugar, protein or fat. Only one dose (12 oz) of water will be ingested. Subjects will not be allowed to crossover from one arm to the other.

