Pre-ingestion or baseline measurements of SpO₂ and heart rate will be measured. At one-minute post ingestion, SpO₂ and heart rate will be recorded. Subjects will complete clinical outcome assessments as patient reported outcome (PRO) for Energy level and Brain clarity assessment at pre- and post-ingestion time points.

Only one clinic visit will be necessary for a subject to complete the study. The overall study design is presented in Figure 1.

[figure not shown]

Fig 1: Study design schema

Sample Size Calculation

The primary outcome measure for the power calculation is the difference between INHALE super-oxygenated water and source and taste-matched placebo control water in the change of SpO₂ and heart rate. There are no prior studies known to the sponsor that measured similar effects following an oral ingestion to better advise sample size calculation. The sample size of 30 is selected to support analysis for an expected >1% increase in SpO₂ and an anticipated >1% decrease in heart rate as continuous measures in the experimental group with an alpha level of 0.05 powered at 80%.

AIMS AND OBJECTIVES

To demonstrate an improvement in blood oxygen saturation and reduction in heart rate following ingestion of super-oxygenated water. Additionally, the study will also measure whether the super-oxygenated water will enhance energy level and brain clarity.

OUTCOMES

Primary and secondary outcome measures will be assessed to answer the study aims and objectives. The analyses of the data are described below.

Primary Outcome Measures

1. Blood oxygen saturation (SpO₂). It will be measured at pre-ingestion and at one-minute post-ingestion of water by a pulse oximeter.
2. Heart rate. It will be measured at pre-ingestion and at one-minute post-ingestion of water by a pulse oximeter.

Secondary Outcome Measures

1. Energy level. It will be assessed at pre-ingestion and at one-minute post-ingestion of water through patient reported outcome measure (PRO) with a questionnaire (scale 1-10).
2. Brain clarity. It will be assessed at pre-ingestion and at one-minute post-ingestion of water through a PRO questionnaire (scale 1-10).

Safety Outcomes

Consumption of water is generally considered safe for human consumption. The sponsor is not aware of any health events related to drinking of super-oxygenated water. The production cycle of INHALE superoxygenated water encompasses a closed and aseptic cycle that ensures consistency and sterility of the product.

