The blood oxygen saturation will be measured twice (before and after water ingestion). The post-ingestion SpO2 will be compared with the pre-ingestion SpO2 from the same subject. An increased post-ingestion SpO2 over the pre-ingestion level will constitute treatment response and the SpO2 response rate (n/N) will be measured for both study arms. Pearson Chi-Square test will be applied to analyze categorical data (SpO2 response rate) between the arms for asymptotic significance (2-sided) at 5% level.

Heart Rate

The heart rate will be measured twice (before and after water ingestion). The post-ingestion heart rate will be compared with the pre-ingestion heart rate from the same subject. A reduction in post-ingestion heart rate over the pre-ingestion level will constitute treatment response and the heart rate response rate (n/N) will be measured for both study arms. Pearson Chi-Square test will be applied to analyze categorical data (heart rate response rate) between the arms for asymptotic significance (2-sided) at 5% level.

Energy Level

Energy level as reported by PRO assessment will be measured twice (before and after water ingestion). The post-ingestion energy level will be compared with the pre-ingestion energy level from the same subject. An increased post-ingestion energy level over the pre-ingestion level will constitute treatment response and the energy level response rate (n/N) will be measured for both study arms. Pearson Chi-Square test will be applied to analyze categorical

data (energy level response rate) between the arms for asymptotic significance (2-sided) at 5% level.

Brain Clarity

Brain clarity as reported by PRO assessment will be measured twice (before and after water ingestion). The post-ingestion brain clarity will be compared with the pre-ingestion brain clarity from the same subject. An increased post-ingestion brain clarity over the pre-ingestion level will constitute treatment response and the brain clarity response rate (n/N) will be measured for both study arms. Pearson Chi-Square test will be applied to analyze categorical data (energy level response rate) between the arms for asymptotic significance (2-sided) at 5% level.

MISSING DATA

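### The responder rule scores worsening the same as no change and ignores size, so the only planned tests do not address the between-arm difference in change that the plan names as its target

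*SAP*

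**What the plan says.** The outcome subsections of ANALYSES in the SAP define response as follows.

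- SpO2: "An increased post-ingestion SpO2 over the pre-ingestion level will constitute treatment response".
- Heart Rate: "A reduction in post-ingestion heart rate over the pre-ingestion level will constitute treatment response".
- Energy Level: "An increased post-ingestion energy level over the pre-ingestion level will constitute treatment response".
- Brain Clarity: "An increased post-ingestion brain clarity over the pre-ingestion level will constitute treatment response".

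No minimum size is set. A subject with no change and a subject who moved the wrong way are both non-responders. Each response rate is compared by Pearson chi-square "between the arms for asymptotic significance (2-sided) at 5% level". No other test is planned for any outcome.

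The Sample Size Calculation section names a different quantity: the difference between INHALE and placebo water in the change of SpO2 and heart rate. It plans for an "expected >1% increase in SpO₂ and an anticipated >1% decrease in heart rate as continuous measures". The trial is "randomized at 1:1 ratio with each arm enrolling 30 subjects".

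The opening of ANALYSES also promises descriptive summaries (percentages, means, standard deviations and/or standard errors, scatter plots, histograms). MISSING DATA fills a missing reading with the subject's other reading, which makes that change exactly zero and so a non-response.

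**The concern.** Each subject can improve, stay the same or worsen. The rule keeps the first category and pools the other two, which has two consequences.

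1. If the water makes some otherwise unchanged subjects worse, the response rate does not move and no planned test registers it.
2. If ties are common, the response rate also depends on how many subjects stayed put. An arm with more scatter has fewer ties and more responders, even when as many subjects fell as rose.

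Both primary conclusions rest on this rule. Followed as written, the plan could report no difference where INHALE subjects did worse, or a benefit where the average change is nil.

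**Working it through.** **The plan's own figure.** For two arms, n per arm = 2(1.960 + 0.842)² SD²/δ². With n = 30 and δ = 1 SpO2 point, SD = √(30 / (2 × 7.849)) = 1.38. The SAP gives no SD of change and no expected response rates, so 30 per arm can be back-solved but neither confirmed nor refuted. The calculation concerns change, not a response rate.

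**Inputs.** From the SAP: 30 per arm, the responder rules, and an uncorrected Pearson chi-square, two-sided at 5%. Assumed: whole-unit readings, normally distributed changes, and all SDs and counts below.

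**Untested worsening.** Improved/unchanged/worsened: INHALE 9/9/12, placebo 9/21/0.

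- Planned test: 9/30 v 9/30, chi-square = 0, p = 1.0.
- Rank test on the three ordered categories: pooled counts are 12 worse, 30 same and 18 better, with midranks 6.5, 27.5 and 51.5. The INHALE rank sum is 12 × 6.5 + 9 × 27.5 + 9 × 51.5 = 789, so U = 789 − 465 = 324 against 450 expected. The tie-corrected SD is 62.0, z = (126 − 0.5)/62.0 = 2.02, p = 0.043 against INHALE.
- Worsened alone: 12/30 v 0/30, chi-square = 15.0, p = 0.0001.

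With true rates of 20/20/60% v 20/60/20%, the planned test finds against INHALE in 2.4% of trials, which is chance level. A Welch t-test on the scores −1/0/+1 does so in 55% (20,000 simulations).

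**Scatter read as benefit.** INHALE 15/0/15, placebo 6/18/6. The net change is zero in both arms. The pooled rate is 21/60 = 0.35, and chi-square = 0.30² / (0.35 × 0.65 × 2/30) = 5.93, p = 0.015 in favour of INHALE. The rank test gives p = 1.0.

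More generally, let the mean change be zero in both arms and round changes to whole units, so that P(response) = 1 − Φ(0.5/SD). Summing over two Binomial(30, p) distributions gives the exact chance of a significant result in favour of INHALE (nominal about 2.5%):

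| SD of change, placebo v INHALE | Response rates | In favour of INHALE |
|---|---|---|
| 0.5 v 0.75 | 16% v 25% | 14% |
| 0.5 v 1.0 | 16% v 31% | 27% |
| 0.5 v 1.5 | 16% v 37% | 46% |
| 0.75 v 1.5 | 25% v 37% | 16% |
| 1 v 1.5 | 31% v 37% | 7% |
| 1 v 2 | 31% v 40% | 11% |
| 4 v 8 (heart rate, bpm) | 45% v 48% | 4% |

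A Welch t-test on the change, simulated for five unequal-SD settings (0.5 v 1, 0.5 v 1.5, 0.75 v 1.5, 1 v 2, 4 v 8), stays at 2.4 to 2.6%. With a true mean fall of 0.5 point on INHALE and SDs of 0.5 v 1.5, the planned test still finds for INHALE in 14% of trials and against it in 0.2%.

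**Uniform worsening (counter-check).** Same SD in both arms, INHALE shifted down:

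| Shift, SD | Planned test finds against INHALE | Welch t on change |
|---|---|---|
| −1, SD 1 | 71% | 96% |
| −0.5, SD 1 | 27% | 44% |

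As a worked table, 2/10/18 v 10/10/10 gives 2/30 v 10/30, chi-square = 6.67, p = 0.0098 against INHALE.

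**The case against.** **The test is two-sided.** A reader might infer that any real worsening is invisible to every planned test. The SAP does not support that. Worsening that removes responders lowers the INHALE rate and can be significant against it, as the counter-check shows. What stands is narrower: worsening drawn from the unchanged group, or offset by wider scatter, goes unseen, and uniform worsening is detected with less power.

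**Nothing suggests wider scatter on INHALE.** Both arms are measured with a pulse oximeter at the same two times, randomised and double-blind, so measurement noise should be alike. If the water does nothing at all, both arms share one response probability and the planned test keeps its size: 4.9 to 5.4% two-sided for response rates from 10% to 50%. A reader might infer that a false positive is likely. That also goes too far, because inflation requires INHALE to alter the spread without improving the mean. The 15/0/15 v 6/18/6 example is an extreme chosen to show the mechanism, and milder settings give far less (7% at SDs 1 v 1.5).

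**The effect differs by outcome.** It depends on ties. It is strong for whole-number SpO2, plausible for the 1-10 scores, and slight for heart rate (4% against 2.5% even with the SD doubled).

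**Descriptive summaries are planned.** Means, SDs and histograms could display falls and unequal spread, so the information is not lost. They are not tests, however, and no conclusion is tied to them.

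These points narrow the claim. They do not answer why the test ignores size and adverse direction when the sample size section targets change on a continuous scale.

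**Conclusion.** The point holds in limited form. On the face of the SAP, all four responder rules merge worsening with no change and discard size, and the only planned tests therefore do not address the difference in change that the sample size section names. That part needs no assumption.

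The numerical consequences are illustrations. Worsening among otherwise unchanged subjects can leave the planned test at p = 1.0 with 12 subjects worse against none. Scatter alone can raise the chance of a favourable result from about 2.5% to between 7% and 46% over the SpO2-like SDs tried, but only to about 4% for heart rate. These figures rest on whole-unit readings, normal changes and SDs that the SAP does not give, and on a variance difference that it does not suggest. The change should be made, because both primary conclusions depend on this rule.

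**What to change.** - **SpO2 and heart rate:** make the between-arm difference in change the primary test, for example ANCOVA of the post-ingestion value on arm and baseline. With baseline in the model, the arm effect is the same whether the post value or the change is the response. This follows the SAP's own sample size section. The comparison figures above used a Welch t-test on change, not ANCOVA.
- **Energy level and brain clarity:** use the same analysis, or a rank test on change. A rank test uses both directions but is not fully immune to unequal spread: with true rates of 50/0/50% v 20/60/20%, simulation on the three categories gave 8.4% two-sided rejection.
- **All four outcomes:** report improved, unchanged and worsened counts per arm, and keep the response rate as supportive.

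Two lighter repairs are not enough. Testing only the three ordered categories still scores a 1-point and a 3-point fall alike. Accepting a higher response rate as benefit only when the worsened rate is not also higher would misfire: with equal true worsened rates of 10 to 30%, the INHALE rate is higher by chance in 41 to 44% of trials.

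The cost is SAP wording and extra table columns, with no new data. The small downside is that the headline is no longer a single responder percentage.

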All adverse events will be collected, graded and reported.

STUDY POPULATION

Study Eligibility- Inclusionary Criteria

1. Legally adult (18 years or older) and either gender (male or female) will qualify
2. Subject must be willing to review and provide an informed consent for participation
3. Subject must agree to the study procedures including water ingestion, and SpO₂ and heart rate measurements

Study Eligibility- Exclusionary Criteria

1. Any active and life-threatening medical condition involving hepatic, renal, cardiac, respiratory, endocrinial, or gastrointestinal systems, or any blood disorder that may confound the study
2. Female subjects those are pregnant, nursing or planning to become pregnant
3. Subjects receiving any experimental medications or have undergone a major surgical procedure in last 30 days
4. Subjects previously utilized the test article (INHALE super-oxygenated water) within the last 24 hours, have undergone bariatric surgery or have received weight-loss medication
5. Subjects with known anemia, hemoglobinopathies or other comorbidities necessitating fluid restriction

Intent-to-treat (ITT)

All randomized study subjects will constitute ITT population. Collected data will be processed without any bias or selection and no subject data will be excluded from the analyses.

Per Protocol (PP)

All randomized study subjects completing the whole study period (completing all study assessments). The PP analyses will be performed in case of subjects not completing the entire study. Analyses of this population is seen as a sensitivity analysis to investigate whether the study conclusions are sensitive to assumptions regarding the pattern of missing data.

ANALYSES

The outcome measures will be presented using descriptive statistics; to summarize and describe the main features of the dataset using simple numbers (by the percent, mean, standard deviation and/or standard error) and graphs (scatter plot, histogram), helping to make large amounts of data understandable.

These analyses will provide a concise overview of characteristics like proportion of responders in a study group.

SpO2

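### The 80% power is claimed for continuous change in SpO2 and heart rate, but both primary tests are chi-squares on response rates, so the claim does not apply to them

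*SAP*

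**What the plan says.** The Sample Size Calculation (under STUDY DESIGN) names a between-arm contrast of changes as the quantity powered, for both SpO2 and heart rate: "The primary outcome measure for the power calculation is the difference between INHALE super-oxygenated water and source and taste-matched placebo control water in the change". It then justifies 30 by a rise of more than 1% in SpO2 and "an anticipated >1% decrease in heart rate as continuous measures in the experimental group", at alpha 0.05 and 80% power. It gives no SD and says that no prior study is known to the sponsor.

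Under ANALYSES, each primary outcome becomes a yes/no response. For SpO2 it is any increase over the subject's own pre-ingestion value. For heart rate, "A reduction in post-ingestion heart rate over the pre-ingestion level will constitute treatment response". Neither definition carries a 1% threshold. The between-arm test for SpO2 is: "Pearson Chi-Square test will be applied to analyze categorical data (SpO2 response rate) between the arms for asymptotic significance (2-sided) at 5% level". The Heart Rate section repeats it.

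Means and SDs appear only in the opening of ANALYSES: "The outcome measures will be presented using descriptive statistics". No between-arm test, estimate or confidence interval for the mean change is planned.

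**The concern.** Power belongs to a particular test of a particular quantity. Here the sizing concerns a difference in mean change, while the tests compare the proportions of subjects who moved at all in the favourable direction. Reducing a change to its sign discards its size, so the power of one analysis does not carry over to the other.

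Two things are at stake. A non-significant chi-square would be read as a negative result from an 80%-powered trial, which the SAP cannot support. A significant one would show only that more subjects moved favourably by some amount, with no planned estimate or interval to compare with the planning effect of more than 1%. Both primary outcomes and the only sample-size justification are affected.

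**Working it through.** **Inputs from the SAP.** 30 per arm, 1:1 (STUDY DESIGN); alpha 0.05, power 80%, effect above 1% (Sample Size Calculation); two-sided 5% Pearson chi-square (ANALYSES). SD of change and response rates: not given.

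**Step 1: the plan's own figure.** It cannot be reproduced without an SD. Solving backwards, a two-sided two-sample t-test with 30 per arm reaches 80% at a standardised difference d = 0.736. If 1% of SpO2 is read as one saturation point, the SD of change is 1/0.736 = 1.36 points.

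**Step 2: carry that effect into the planned test.** Assume normal changes, equal SDs and zero mean change on placebo.

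- Placebo response: Φ(0) = 0.500. Active response: Φ(0.736) = 0.769. Difference 0.269; pooled rate 0.6345.
- SE under the null: √(2 × 0.6345 × 0.3655 / 30) = 0.1243. SE under the alternative: √((0.769 × 0.231 + 0.500 × 0.500) / 30) = 0.1194.
- Power ≈ Φ((0.269 − 1.96 × 0.1243) / 0.1194) = Φ(0.21) = 0.58. Exact enumeration of the uncorrected Pearson rejection region gives 0.584.
- For 80%, n per arm = [(1.96 × √(2 × 0.6345 × 0.3655) + 0.842 × √(0.769 × 0.231 + 0.25)) / 0.269]² ≈ 49.1, so 50.

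**Step 3: vary the SD for a 1-point SpO2 difference** (30 per arm, no mean placebo change). Whole-number means the change is rounded to an integer and ties count as non-response.

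| Assumed SD | t-test | Chi-square, unrounded | Chi-square, whole-number |
|---|---|---|---|
| 1.0 | 97% | 82% | 87% |
| 1.2 | 89% | 68% | 73% |
| 1.5 | 72% | 51% | 54% |
| 2.0 | 48% | 33% | 34% |

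**Step 4: hold d at 0.736 and vary the other assumptions.**

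- Whole-number changes: 54.5% at SD 0.5; 59–62% at SD 0.75–8.
- Placebo drift in the favourable direction: 0.5 SD (89.2% vs 69.1% responders) gives 49%; 1 SD (95.9% vs 84.1%) gives 35%. Drift of 0.5 SD the other way gives 62%.
- Heavier tails: Laplace changes (82.3% vs 50.0%) give 77%; t(3) changes (85.4% vs 50.0%) give 86%.

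**Step 5: heart rate.** The SAP gives no baseline, so assume 60, 70 or 80 bpm. One per cent is 0.6, 0.7 or 0.8 bpm. Dividing by 0.736, the 80% implies an SD of change of only 0.82, 0.95 or 1.09 bpm. With whole-number changes the chi-square then has 60%, 61% or 62%.

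**Step 6: what the chi-square would need.** For 80% at 30 per arm, with placebo response of 10, 20, 30, 40, 50 or 60%, active response must be about 40, 54, 65, 75, 83 or 90%. That is a gap of roughly 30 to 35 percentage points. The SAP states no such expectation.

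**The case against.** A responder endpoint is legitimate, and this mismatch does not affect the type I error of the chi-square. The sponsor also says openly that nothing was available to inform the sizing. All of that stands, but none of it makes the 80% apply to the planned tests.

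The size of any loss is not determined. At an SD of 1.0, or with t(3) changes, the chi-square exceeds 80%. This stands too, which is why the finding is that the claim does not apply, not that the trial is shown to be underpowered. The whole-number figures are also simplified: they round the change, not each reading, and ignore the 100% ceiling on SpO2.

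The basis of the 80% is itself open to another reading. The sentence carrying it refers to the experimental group, and the INTRODUCTION compares with pre-ingestion levels, so a within-arm paired calculation on 30 subjects is possible. That would imply d = 0.53 (SD 1.89 for one point), and the between-arm chi-square would have about 36%. This changes the illustration but keeps the mismatch. It also conflicts with the same section's statement that the quantity powered is the difference between arms.

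Finally, if means and SDs of change are tabulated by arm, a reader could work out the difference in mean change. That is fair, but it does not replace a planned estimate with a confidence interval.

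**Conclusion.** The concern holds and must be fixed. The contradiction is in the SAP's own text and needs no assumed figure: the 80% is claimed for continuous change, and the only between-arm test of either primary outcome is a chi-square on response rates. The power of both primary tests is unknown and cannot be derived from the SAP.

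The figure of about 58% is conditional on a two-sided t-test at exactly 80%, normal changes with equal SDs, and no mean change on placebo. It illustrates how far the two analyses can diverge; it is not an estimate of this trial's power.

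**What to change.** Align the sizing and the primary analysis in one of two ways.

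1. **Make continuous change primary.** For SpO2 and for heart rate, fit a linear model of the change (or the post-ingestion value) with arm and the pre-ingestion value as covariates. Report the adjusted mean difference with a 95% CI, and keep the response rates as supportive. State the SD of change behind the 80%, mark it as an assumption because no prior studies are known, and show power over a range of SDs. Say whether 1% of SpO2 means a relative change or one saturation point.
2. **Keep the chi-square primary.** Remove the 80% claim, state the assumed response rate in each arm for each primary outcome, and give the power at 30 per arm that follows.

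Either resolves the contradiction. The first also yields an estimate on the scale used for planning.

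The cost is SAP wording, to be settled before unblinding. Pre- and post-ingestion values are already collected, so no new data or subjects are needed. If the protocol, not seen here, names the response rates as the primary analysis, the first option may also need a protocol amendment. The sponsor gives up the responder percentage as the headline result under the first option, and under either must write down assumptions it has not yet stated.

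### Does the Brain Clarity paragraph, whose test sentence names the energy level response rate, leave brain clarity without a specified test?

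*SAP*

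**What the plan says.** The SAP lists brain clarity as the second of two secondary outcomes (Secondary Outcome Measures), separate from energy level. Both appear in the aims: "Additionally, the study will also measure whether the super-oxygenated water will enhance energy level and brain clarity". For methods, the OUTCOMES section points forward: "The analyses of the data are described below".

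Under ANALYSES, four paragraphs (SpO2, Heart Rate, Energy Level, Brain Clarity) share one template. Each defines a responder from the subject's own change, sets up a response rate per arm, and then names the rate that the chi-square test compares. The Brain Clarity paragraph sets up its rate as follows: "An increased post-ingestion brain clarity over the pre-ingestion level will constitute treatment response and the brain clarity response rate (n/N) will be measured". Its test sentence is "Pearson Chi-Square test will be applied to analyze categorical data (energy level response rate) between the arms for asymptotic significance (2-sided) at 5% level".

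**The concern.** A pre-specified test should name the variable it tests. Here the variable defined and the variable tested differ within two consecutive sentences. This is also the only sentence in the SAP that gives a between-arm test for brain clarity. The opening text of ANALYSES covers descriptive summaries and responder proportions only, and MISSING DATA covers imputation only.

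On the literal reading, the energy level comparison is specified twice and the brain clarity comparison not at all. If that reading were tenable, one of two secondary outcomes would be analysed without a pre-specified rule, and the choice of test could be made after the data were seen.

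**Working it through.** No sample size, power or alpha figure is involved, so the check is a comparison of the four paragraphs under ANALYSES.

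**Step 1. Rate defined against rate tested**

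| Paragraph | Rate defined | Rate named in the test sentence | Match |
|---|---|---|---|
| SpO2 | SpO2 | SpO2 | yes |
| Heart Rate | heart rate | heart rate | yes |
| Energy Level | energy level | energy level | yes |
| Brain Clarity | brain clarity | energy level | no |

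The first two test sentences begin "Pearson Chi-Square test will be applied to analyze categorical data (SpO2 response rate) between the arms" and "Pearson Chi-Square test will be applied to analyze categorical data (heart rate response rate) between the arms". The Energy Level sentence ends "data (energy level response rate) between the arms for asymptotic significance (2-sided) at 5% level". The Brain Clarity sentence ends in exactly the same words, so the section heading, not the wording, tells the two apart.

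**Step 2. Count of mentions (definitions + test sentences)**

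- SpO2: 1 + 1 = 2
- Heart rate: 1 + 1 = 2
- Energy level: 1 + 2 = 3
- Brain clarity: 1 + 0 = 1

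The total is 2 + 2 + 3 + 1 = 8, which is what four definitions and four test sentences should give. The template implies 2 each. One mention has moved from brain clarity to energy level, and the four test sentences name three distinct outcomes. This is the pattern that one uncorrected copied bracket would leave.

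**Step 3. Is the literal reading tenable?** It would require the authors to have meant the following:

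1. to state the energy level test in its own paragraph and then again, word for word, under another outcome's heading;
2. to define a brain clarity responder and a rate for both arms, and then not compare them;
3. to break, in the last paragraph only, a pattern kept in the other three.

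The repeated energy level test would use the same data and give the same p-value, so it would serve no purpose. The reading is grammatically possible but not credible.

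**Step 4. What depends on the bracket?** Once the brain clarity responders are counted in each arm, the 2×2 table is fixed. The rest of the sentence supplies the method: Pearson chi-square, between arms, two-sided, 5%. The same method applies to all four outcomes, so there is no competing test to choose from. Each outcome is tested at its own 5% level, so the other three tests do not depend on how this sentence is read. The ITT and PP definitions and the imputation rule are set elsewhere and are unaffected.

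**The case for a change.** The strongest case for a change is that the sentence is wrong as written, nothing else in the SAP puts it right, and an analysis plan exists so that nobody has to infer what is tested. The correction would be a single phrase with no knock-on effect. The fault also cannot be put down to text extraction, which may break a line but would not plausibly swap one outcome's name for another.

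All of that stands as a description of the text. What does not stand is the suggested consequence, a missing analysis for a secondary outcome. The inference needed is from a heading and the sentence immediately before, not from outside knowledge, and only one answer is reasonable. There is no set of alternative analyses among which someone could choose after seeing the results. That the edit is cheap does not show that it gains anything: the analysis performed would be the same with or without it.

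**Conclusion.** The wording is wrong, but no change to the plan follows. This is a clerical slip confined to one bracketed phrase in one of four parallel test sentences, for a secondary outcome. The intended analysis, a two-sided 5% Pearson chi-square comparison of the brain clarity response rate between arms, can be recovered from the paragraph itself. No result or conclusion would differ after correction.

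The conclusion rests on two assumptions. The first is that the bracket was copied from the Energy Level paragraph, which the SAP does not say but the identical wording strongly supports. The second is that the analyst reads the sentence together with its heading and the definition before it. It concerns only the misnamed variable and does not assess whether the responder definition or the chi-square test is a good choice.
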